Study Protocol and Statistical Analysis Plan

(Version: 2.0 Date: 2023.3.28)

Name: Construction of Symptom Network in Maintenance Hemodialysis Patients

Applicant: Ren Ji Hospital, Shanghai Jiao Tong University School of Medicine

Principal investigator: [name]

Objective

Through a cross-sectional questionnaire survey, a general information questionnaire and Dialysis Frequency, Severity, and Symptom Burden Index were used to investigate the frequency, severity, and degree of symptom distress in MHD patients, and to analyze the differences in symptom distress status between long and short dialysis age MHD patients. Using the R 4.2.2 software qgraph package, construct symptom networks for MHD patients of long and short dialysis age through network analysis. Analyze network centrality indicators, including intensity, closeness centrality, and mediation centrality, to identify core symptoms and compare if there are any differences between the two groups, aiming to lay the foundation for precise and efficient phased symptom management.

Background

End stage renal disease (ESRD) is caused by various kidney diseases, leading to irreversible decline in renal function. The main renal replacement therapy (RRT) for ESRD is hemodialysis (HD), peritoneal dialysis (PD), and kidney transplantation. Due to the impact of kidney supply on kidney transplantation, it is limited in clinical practice, and hemodialysis has become the most common method of RRT in most countries. According to the registration system of the Chinese Research Data Services (CNRDS), as of the end of 2021, there were 751098 dialysis patients and 155738 new patients in China, with an average dialysis age of 50.9 months. The proportion of patients with dialysis age greater than 5 years was 31.5%. There are a large number of hemodialysis patients with a longer dialysis age.

With the continuous development of dialysis technology, the survival rate of maintenance hemodialysis (MHD) patients is becoming higher and higher. However, MHD patients may experience various symptoms during long-term treatment, which is the main cause of discomfort and physical and mental health for patients. The physical and mental pain or torment experienced by patients due to the disease itself and/or the symptoms caused by treatment is called symptom distress. Multiple studies have shown that the incidence of symptom distress in MHD patients ranges from

13.75% to 91.5%, which is at a high level. Symptom distress is negatively correlated with the quality of life of MHD patients. Excessive symptom distress increases the cost of treatment and exacerbates the psychological burden on patients. Persistent symptom burden can significantly affect the quality of life of MHD patients and increase their mortality rate. MHD patients suffer from multiple symptoms at the same time. Li Jiuhong et al.'s research results show that MHD patients experience a total of 3-25 (13.12 ± 5.27) symptoms, which is similar to Weisbord et al.'s average of 9 symptoms. MHD patients experience a wide variety of symptoms, and how to accurately and effectively manage symptoms is the future research direction.

With the prolongation of dialysis treatment time for patients, some urea toxin that cannot be completely cleared by dialysis accumulates in the patient's body, which is closely related to discomfort symptoms such as itching, joint pain, and difficulty falling asleep. Ran Yuli et al. found that the dialysis age of MHD patients is negatively correlated with their physical function and role. With the prolongation of dialysis age, the physiological function of MHD patients will decrease to varying degrees, and various disease-related complications will also occur. The focus of symptom management will shift accordingly. Conducting grouping studies based on dialysis age for MHD patients has certain clinical significance. At present, domestic scholars use a 5-year hemodialysis period as the boundary, dividing dialysis age >5 years into long dialysis age, and dialysis age ≤ 5 years into short dialysis age. Hu Qian and others set up symptom management consultants to develop symptom management pathways and guide responsible nurses to implement symptom management for patients according to the pathway table. The results indicate that setting up symptom management consultants can reduce the incidence of symptoms in MHD patients, improve their quality of life, and improve patient satisfaction. A meta-analysis showed that aerobic exercise can improve several symptoms related to hemodialysis in adults receiving MHD, including restless leg syndrome, depressive symptoms, muscle spasms, and fatigue. Zhao Ying et al. used air wave pressure therapy to prevent dialysis related muscle spasms, Zuo et al. managed symptoms of fatigue through nurse led non drug multidisciplinary holistic care, Beerappa et al. improved sleep

disorders in MHD patients through aromatherapy, Guo Junjun et al. improved fatigue symptoms and alleviated sleep disorders in MHD patients through acupoint massage. When conducting symptom management for MHD patients, existing studies have not distinguished the age of dialysis, and currently, symptom management for MHD patients mainly focuses on a single symptom or symptom group, ignoring the interaction between multiple symptoms in the real world. In real clinical situations, patients often have multiple symptoms at the same time, and it is urgent to identify the core symptoms of patients to improve the accuracy and efficiency of symptom management.

With the development of information technology, big data analysis technology, and the innovation of complex scientific research concepts in the real world, the concept of symptom networks is gradually replacing the previous research paradigm that focuses on individual symptoms and must control other variables. Symptom network is a collective representation of symptoms related to a patient's disease, and based on complex network analysis to quantitatively study the correlation between different symptoms. It studies the network structure, nodes, and network indicators composed of individual symptoms to reflect the interaction mechanism of symptoms in the real world and provide precise intervention targets. Discovering core symptom targets through symptom networks can improve the management efficiency and intervention accuracy of symptom management, evolving from the working mode of "having multiple symptoms and providing multiple sets of intervention measures" to "identifying intervention targets and providing intervention measures targeting target symptoms". Since Fried et al. first proposed the concept of symptom networks in 2015, the research paradigm of symptom networks has been applied in psychopathology, chronic disease symptom management, long-term follow-up of tumors, and patient self-management. Lin et al. constructed a self-reported psychological and neurological symptom network for head and neck cancer patients through network analysis. The results showed that network analysis clarified the interrelationships between five psychological and neurological symptoms, and identified depression as the core symptom. It is recommended to develop symptom

management measures for depression in clinical practice. Han et al. constructed symptom networks for autism and schizophrenia. Yang Hongli et al. applied symptom networks to HIV infected individuals and identified fatigue as the core symptom. They suggested that when HIV infected individuals have multiple symptoms at the same time, high-intensity and precise intervention on fatigue can reduce the transmission of fatigue as a mediating bridge in the symptom network, reduce the severity of fatigue symptoms, and also alleviate the severity of other symptoms. As mentioned above, symptom network analysis can identify core symptoms, and changing these core symptoms may be an important entry point for changing the entire network. In practical clinical work, implementing key interventions by nurses on core symptoms can more effectively improve other related symptoms and improve intervention efficiency. Applying symptom networks to the field of symptom management is a promising and precise technology in real-world clinical settings.

This study has developed a symptom distress questionnaire for maintenance hemodialysis patients. Previous literature on symptom distress and symptom management in MHD patients has been reviewed. Whether there are differences in symptom distress among MHD patients of different dialysis ages, and how to identify the core symptoms of MHD patients of different dialysis ages through symptom networks to improve the accuracy and effectiveness of intervention are all directions that need to be studied in the future. The research hypotheses of this study are: ① There are differences in the frequency, severity, and degree of symptom distress between long and short dialysis age MHD patients; ② By using network analysis methods to construct symptom networks for long and short dialysis age MHD patients, identify the core symptoms of different dialysis age MHD patients. Based on literature review and clinical experience, it is assumed that the core symptoms of long dialysis age MHD patients are itching or dry skin, while the core symptoms of short dialysis age MHD patients are fatigue or dry mouth.

Contents

1. Current survey of symptom burden in maintenance hemodialysis patients

① Understanding the current status of symptom distress in maintenance hemodialysis patients through cross-sectional questionnaire survey

② Comparative analysis of symptom distress in maintenance hemodialysis patients with long and short dialysis age

2. Construction of symptom network and core symptom recognition for maintenance hemodialysis patients

① A multicenter study on the current status of symptom distress in maintenance hemodialysis patients

② Construct symptom networks for long-term, short-term, and all maintenance hemodialysis patients using network analysis based on cross-sectional survey data from multiple centers

③ Identify and analyze the core symptoms of long dialysis age, short dialysis age, and all maintenance hemodialysis patients based on network centrality parameters

Methods

Participants

Convenient sampling method was used to select MHD patients from six blood purification centers, including the East, West, South, Baoshan Branch, Ningbo Hangzhou Bay Branch, and Punan Hospital of Renji Hospital Affiliated to Shanghai Jiao Tong University School of Medicine.

(1) Inclusion criteria: ① Age not less than 18 years old; ② Regular hemodialysis time greater than or equal to 3 months; ③ The dialysis plan did not change within one month; ④ Informed consent and voluntary participation in this study.

(2) Exclusion criteria: ① Previous or current mental illness; ② Cognitive impairment; ③ Acute cardiovascular and cerebrovascular disease; ④ Acute infection period; ⑤ Complications such as severe cerebrovascular sequelae and tumors.

(3) Sample size and calculation method: The Dialysis Frequency, Severity, and Symptom Burden Index for dialysis patients used in this study includes a total of 30 symptoms. When constructing a symptom network model, the threshold parameters

that need to be estimated are 30, paired association parameters are $30 \times \frac{(30-1)}{2} = 435$, and the total parameters are $30 + 435 = 465$. Therefore, the sample size needs to be at least 465. Considering 10% of invalid samples, the sample size of this study is at least $465 \div (1 - 10\%) = 517$.

Instruments

General Information Questionnaire: Designed by the researchers themselves, including laboratory examination indicators such as gender, age, dialysis age, marital status, educational level, work status, residential status, medical expense payment method, economic burden, primary disease, comorbidities, recent medication, hemoglobin, etc.

Dialysis Frequency, Severity, and Symptom Burden Index(DFSSBI) : DFSSBI is an adaptation of the Dialysis Symptom Index (DSI) developed by Weisbord et al., using the symptom management theory model as the theoretical framework, by American scholars Danquah et al., which increases the frequency of symptoms and the degree of distress in two dimensions. This scale has been proven to have good reliability and validity in foreign countries. Cronbach's α The coefficient is 0.923, the content validity coefficient is 0.939, and the retest reliability is 0.83. It has good internal consistency, stability reliability, and structural validity. The scale consists of 30 items, including 25 physiological symptoms such as fatigue, dry skin, itching, etc; Psychological symptoms include sadness, irritability, tension, etc., totaling 5 symptoms. The appearance of symptoms is obtained in the form of "having" and "not having". The frequency and severity of occurrence are evaluated using a Likert 4 level score, with values ranging from "occasional/mild" to "always/very" ranging from 1-4 points. The degree of distress is evaluated using a Likert 5 level score, with values ranging from 0-4 points from "no impact" to "very serious" ranging from 0-360 points. The higher the score, the heavier the individual's burden of symptoms. Zhou Xiaojuan et al. used the Chinese version of DFSSBI to investigate the symptom burden of hemodialysis patients, and their Cronbach's α The coefficient is 0.89, and the retest reliability is 0.91, indicating that the scale is suitable for application in domestic

hemodialysis patients.

Data Collection

Before the investigation, obtain the consent of the hospital ethics committee and departments, explain and communicate with the survey subjects. On dialysis day, researchers will use unified guidelines to explain the research purpose and explain the answer methods and precautions for each question to the survey subjects. The questionnaire is filled out by the patient themselves. For survey subjects who are unable to independently complete the questionnaire, the researcher can collect data through one-on-one Q&A. Collect and check for any missing items on the spot, and promptly supplement and complete them.

Statistical Analysis Plan

Enter the collected information into the database established by Epidata 3.1, and after verification, import it into SPSS 21.0 software for data analysis. The patient's gender, marital status, education level, work status, and other counting data are described using frequency and percentage. Age, hemoglobin, blood phosphorus, and other measuring data that meet normality are represented by mean and standard deviation, while those that do not meet normality are represented by median and interquartile spacing. The symptom distress scores of MHD patients with different characteristics were tested for normality and homogeneity of variance. If they obey the normal distribution and have the same variance, t-test and analysis of variance were used. Otherwise, nonparametric rank sum test was used. Use R4.2.2 software qgraph package for network analysis to generate complex network descriptions of the relationship between symptoms. Use network centrality indicators such as strength, tight centrality, and mediation centrality to represent the degree of interconnection of symptom networks. The intensity reflects the total direct connection between symptoms and other symptoms, that is, the ability of symptoms to affect other symptoms; The closeness centrality reflects the reciprocal of the distance between symptoms and other symptoms, that is, the core position of symptoms in the network; Mediation centrality reflects the number of shortest paths through the symptom, which serves as a bridge between the symptoms in the network.

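### The all-patient network names a core symptom with no stated adjustment for dialysis age; if several symptoms differ by about 0.5 SD or more between groups, that alone can change the answer

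*Combined protocol and SAP*

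**What the plan says.** Contents, part 2, item ② plans three networks: "Construct symptom networks for long-term, short-term, and all maintenance hemodialysis patients using network analysis based on cross-sectional survey data from multiple centers". Item ③ then asks the analyst to "Identify and analyze the core symptoms of long dialysis age, short dialysis age, and all maintenance hemodialysis patients based on network centrality parameters". The all-patient core symptom is therefore a deliverable in its own right, although the Objective and hypothesis ② speak only of the two dialysis-age groups.

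Hypothesis ①, at the end of the Background, is that "There are differences in the frequency, severity, and degree of symptom distress between long and short dialysis age MHD patients". The Background describes the split as "dividing dialysis age >5 years into long dialysis age, and dialysis age ≤ 5 years into short dialysis age".

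On interpretation, the Background says of the symptom network: "It studies the network structure, nodes, and network indicators composed of individual symptoms to reflect the interaction mechanism of symptoms in the real world", and adds that this yields targets for intervention. The Statistical Analysis Plan says "The intensity reflects the total direct connection between symptoms and other symptoms" and equates this with a symptom's capacity to influence the others.

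On method, the Statistical Analysis Plan says only: "Use R4.2.2 software qgraph package for network analysis to generate complex network descriptions of the relationship between symptoms". It does not say which score forms a node (presence, frequency, severity, distress or a total), which estimator is used, or whether dialysis age enters the all-patient network. The parameter count in the sample-size paragraph covers 30 symptom thresholds and 435 symptom pairs, with no term for dialysis age.

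**The concern.** When two groups with different means are pooled, any two symptoms that both differ between the groups become correlated, whether or not they are related within either group. Such a link reflects who was pooled. It does not show that one symptom acts on another, yet the plan reads its edges and strength values in that way.

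If several symptoms shift in the same direction with dialysis age, each gains strength from its links with the others. The all-patient ranking is then pulled towards the symptoms that separate the groups most. A finding about levels (hypothesis ①) could reappear as a core symptom and be taken up as an intervention target. The pull has a direction, so recruiting more patients does not remove it.

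**Working it through.** **The plan's own figure.** 30 × 29 / 2 = 435 pairs; 30 + 435 = 465; 465 / 0.9 = 516.7, rounded up to 517. This reproduces exactly and contains no parameter for dialysis age.

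**Inputs.**
- Share with long dialysis age: p = 0.315. The Background says "The proportion of patients with dialysis age greater than 5 years was 31.5" per cent; this is a national registry figure, assumed here for a convenience sample.
- Analysable patients: N = 465 (sample-size paragraph).
- Shift d, in within-group SDs: not given anywhere, so a range is shown.

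**Link created by pooling.** With v = p(1 − p) = 0.315 × 0.685 = 0.2158, two symptoms unrelated within groups and each shifted by d have pooled correlation r = v·d² / (1 + v·d²).

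| d | v·d² | r |
|---|---|---|
| 0.3 | 0.0194 | 0.019 |
| 0.5 | 0.0539 | 0.051 |
| 0.8 | 0.1381 | 0.121 |

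If the groups were equal in size (p = 0.5), the values would be 0.022, 0.059 and 0.138. Two yardsticks help. The standard error of a correlation near zero is about 1/√465 = 0.046. The mean inter-item correlation implied by the alpha of 0.89 quoted under Instruments, if it refers to all 30 items, is 0.89 / (30 − 0.89 × 29) = 0.89 / 4.19 = 0.21.

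If nodes are present/absent, the induced phi is about 0.009, 0.035 and 0.079 for prevalence gaps of 10, 20 and 30 points around 50%.

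**Accumulation into strength.** If k symptoms shift together and are otherwise independent, write a = v·d². Each partial correlation among them is a / (1 + (k − 1)a), and each shifted symptom gains (k − 1) times that in strength:
- k = 5, d = 0.3: 4 × 0.0180 = 0.07
- k = 5, d = 0.5: 4 × 0.0444 = 0.18
- k = 5, d = 0.8: 4 × 0.0890 = 0.36
- k = 10, d = 0.5: 9 × 0.0363 = 0.33

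**Does the top symptom change?** Sparse 30-node networks, identical in both groups apart from the mean shift, were simulated at N = 465 and p = 0.315. The network structure is assumed. The table shows how often unadjusted and group-centred data named different top-strength symptoms.

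| Symptoms shifted | d | Partial correlations | Plain correlations |
|---|---|---|---|
| none | – | 6.5% | 2.2% |
| 5 | 0.3 | 10.5% | 5.0% |
| 5 | 0.5 | 22.5% | 13.8% |
| 5 | 0.8 | 46.8% | 27.0% |
| 10 | 0.5 | 31.2% | 33.5% |
| 30 | 0.3 | 22.0% | 47.0% |

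The last row is a limiting case: a small shift matters only when it is shared across the whole scale.

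**A second design.** Here all 30 symptoms were equal within groups (r = 0.21) and 8 were shifted the same way. A shifted symptom came top in 30–33% of samples at d = 0.3, 45–46% at d = 0.5 and 66–74% at d = 0.8. Chance is 8/30 = 27%, and after centring within group the figure was 24–28%. This design has no true core symptom to displace, so it shows the direction of the pull and overstates its consequence. With unequal loadings and 8 shifted symptoms, recovery of the true core symptom barely changed at d of 0.5 or less.

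**After adjustment.** Centring makes the group means equal, so d = 0 and the induced link is 0.

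**The case against.** The strongest reply is that the pooled network is a legitimate description of a mixed patient population, and that the Background itself presents networks as a departure from controlling for other variables. That stands for description. It does not cover reading the result as interaction or as an intervention target, which the plan also does.

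Four further points have force.
- **Raw scores.** A reader might infer that the plan pools raw scores. The documents do not say so: node score, estimator and covariates are all unstated. The defect is an omission.
- **Hypothesis ① as sufficient.** A reader might infer that the bias follows whenever hypothesis ① is true. It does not. The hypothesis gives no size and no list of symptoms. One shifted symptom creates no link, and at 0.3 SD the induced correlation of 0.019 lies well inside the sampling error of 0.046.
- **Sampling noise is larger.** With no shift at all, two simulated samples of 465 disagreed on the top symptom in 77–89% of runs. That is true, but noise favours no particular symptom, whereas this effect does.
- **Why dialysis age alone?** Age, sex or centre could shift symptom means in the same way, including inside the two group networks, and one cut at 5 years leaves variation within groups. This is fair. Dialysis age is singled out because the plan itself predicts a level difference on it.

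Adjustment also has a cost. Centred item scores are no longer ordinal, so one recipe will not suit every node type. A group node would raise the plan's own count to 31 + 31 × 30 / 2 = 496, and 496 / 0.9 rounds up to 552 rather than 517.

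**Conclusion.** The point holds as a conditional one. The plan names an all-patient core symptom with no specified adjustment for dialysis age while expecting levels to differ by dialysis age. If several symptoms shift together by about 0.5 SD or more, the level difference adds links of about 0.05 (0.5 SD) to 0.12 (0.8 SD) and can change the top-strength symptom. With five symptoms shifted, adjusted and unadjusted partial-correlation networks disagreed in roughly 22% to 47% of simulated samples, against 6.5% with no shift. For a handful of symptoms at 0.3 SD or less the effect is negligible.

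These sizes rest on assumed shifts, assumed network structures and the national 31.5% share. The mechanism does not depend on those choices, but its importance in this sample cannot be known in advance.

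A reader might go further and doubt the long and short dialysis-age networks, or hypothesis ②. The documents do not support that: each of those networks is fitted within one group, so this between-group shift cannot enter it. Nor does the point make the unadjusted all-patient network invalid. It limits what may be concluded from it.

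**What to change.** State the node score and estimator in the Statistical Analysis Plan, then add that the all-patient network will be fitted both unadjusted and adjusted for dialysis-age group.
- For nodes treated as continuous, centre or residualise each score within group.
- For ordinal or binary nodes, add dialysis-age group as a covariate node and exclude its edges from the symptom centrality indices.

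Report both networks. Label the unadjusted one as a description of the mixed population. Interpret an all-patient core symptom as an interaction or intervention target only if it holds in the adjusted network.

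The cost is a sentence or two of text and one extra network fit. Dialysis age is already on the General Information Questionnaire, so no new variable is collected. A covariate node adds up to 30 edge parameters (31 with its own threshold). If the sponsor keeps its rule of one patient per parameter, the plan should say whether that rule applies to the adjusted network as well; centring within group avoids the question.

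### Patients are selected by convenience although the plan aims to describe the symptom status of MHD patients and to compare dialysis-age groups; consecutive roster-based invitation with a simple log would be a cheap improvement

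*Combined protocol and SAP*

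**What the plan says.** - **Selection (Methods, Participants):** "Convenient sampling method was used to select MHD patients from six blood purification centers".
- **Descriptive aim:** the Objective sets out "to investigate the frequency, severity, and degree of symptom distress in MHD patients". Contents item 1 ① reads "Understanding the current status of symptom distress in maintenance hemodialysis patients through cross-sectional questionnaire survey", and Contents item 2 ① repeats it across centres: "A multicenter study on the current status of symptom distress in maintenance hemodialysis patients".
- **Comparison:** hypothesis ①, at the end of the Background, expects frequency, severity and distress to differ between long and short dialysis age.
- **Occasion (Data Collection):** "On dialysis day, researchers will use unified guidelines to explain the research purpose". Inclusion criterion ④ requires "Informed consent and voluntary participation in this study".
- **Help with completion (Data Collection):** "For survey subjects who are unable to independently complete the questionnaire, the researcher can collect data through one-on-one Q&A". Forms are also checked for missing items on the spot.

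The plan describes no sampling frame, consecutive or random selection, coverage of shifts, rule for a second approach, log of eligible or declining patients, comparison of participants with non-participants, or weighting. The Statistical Analysis Plan section contains no analysis of selection.

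**The concern.** A statement of the current status of symptoms in MHD patients is an estimate about a population. Convenience selection gives no defined link between that population and the patients surveyed.

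This has more force here than in most surveys because the outcome could itself influence selection. Fatigue is an item on the scale, and the Background names muscle spasms and sleep disorders among these patients' symptoms. Such problems could plausibly affect who is approachable, or willing, during a session.

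Two results are at stake. One is the reported frequencies and scores. The other is the dialysis-age comparison, which would be distorted if selection depended on symptoms differently in the two groups. Without a record of who was missed in each group, a reader could not judge this well.

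**Working it through.** **1. The plan's own figure.** The sample size is a parameter count: 30 + 30 × 29 / 2 = 30 + 435 = 465, and 465 / 0.9 = 516.7, rounded up to 517. It reproduces. It comes only from the network model, so it says nothing about representativeness.

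**2. Sampling error at 465 valid forms.** The 95% half-width is 1.96 / √465 = 0.09 SD for a mean, and 1.96 × √(0.5 × 0.5 / 465) = 4.5 percentage points for a symptom present in 50%.

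**3. Selection error, simple form.** Bias = (1 − share reached) × (difference between reached and unreached patients). The documents give neither input. Assuming a 10-point difference in prevalence, the bias is 5.0, 3.0 and 1.0 points when 50%, 70% and 90% are reached. Assuming 20 points, it is 10.0, 6.0 and 2.0. The sample size does not enter the formula.

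**4. Selection error, graded form.** Let burden S be standard normal, with P(surveyed) = 1 / (1 + exp(−(a + b·S))), b = ln(odds ratio per SD), and a solved to give the stated uptake. The odds ratios and uptakes are assumptions.

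| Uptake | Shift in mean, OR 0.9 to 0.7 (SD) | 50% symptom reported as |
|---|---|---|
| 40% | −0.06 to −0.21 | 47% to 42% |
| 60% | −0.04 to −0.14 | 48% to 44% |
| 80% | −0.02 to −0.07 | 49.2% to 47.2% |
| 90% | −0.01 to −0.035 | 49.6% to 48.6% |

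At an odds ratio of 0.7 and 40–60% uptake, the shift exceeds the half-widths in step 2. At 0.9, and throughout the 80–90% rows, it does not. The minus signs follow from choosing odds ratios below 1. Because S is symmetric, the inverse odds ratios give upward shifts of equal size.

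**5. Group comparison.** If selection acts equally in both dialysis-age groups, the shifts cancel in the difference. If, as an assumption, uptake is 60% in both but the odds ratio is 0.9 in one and 0.7 in the other, the spurious difference is 0.139 − 0.042 = 0.097, about 0.10 SD.

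**6. Networks.** In the most extreme case above (odds ratio 0.7, 40% uptake), the variance of S falls from 1.00 to 0.971. With one common factor and an assumed between-symptom correlation of 0.30, the correlation becomes 0.30 × 0.971 / (0.30 × 0.971 + 0.70) = 0.294. The change of 0.006 is about one seventh of the standard error of a correlation at n = 465, which is (1 − 0.30²) / √464 = 0.042.

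**The case against.** The strongest reply is that the mechanism is conjecture, and much of it stands.

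- **Passing over the unwell.** A reader might infer that sites skip patients who are asleep, cramping or exhausted, or leave shifts unstaffed. No text says so. The plan places the survey at a dialysis session but does not limit a patient to one chance.
- **Direction.** A reader might infer that burden is understated. The documents do not support this either: convenience selection could also favour patients keen to report complaints.
- **State on the day.** The scale rates frequency from occasional to always, so how a patient feels at one session need not track the total score closely.
- **Exclusions.** Some selection of healthier patients comes from the eligibility criteria, such as "Acute cardiovascular and cerebrovascular disease; ④ Acute infection period". These define the target population and would remain under any sampling method.
- **Detectability.** It would be too strong to say that nothing collected could reveal selection. The questionnaire records age, dialysis age, primary disease, comorbidities and hemoglobin. The Background gives national figures for dialysis patients (mean dialysis age 50.9 months, 31.5% above 5 years). Composition can be compared with these, although selection driven by symptoms would be only partly visible.

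The one-on-one Q&A is a genuine safeguard for patients who cannot complete the form, but it applies to people who are already survey subjects. Six centres widen the source without governing who is approached within each. The plan discloses its method openly, but that does not make the method suited to a descriptive aim.

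**Conclusion.** The mismatch between a population-descriptive aim, with a group comparison, and convenience selection is real and merits a cheap improvement. It does not show that the results will be biased by any particular amount or in any particular direction.

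On the assumed odds ratios, the mean would move by about 0.04 to 0.21 SD at 40–60% uptake and 0.01 to 0.07 SD at 80–90% uptake. It can therefore outweigh sampling error or be minor, depending on coverage that the plan neither sets nor records. More patients would not reduce it.

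A reader might also infer that the symptom networks are compromised. Under this model the effect on correlations is negligible, so the point rests on the descriptive aim and the dialysis-age comparison alone.

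**What to change.** In Methods, Participants, replace convenience sampling with consecutive invitation:

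- Work through each centre's dialysis roster across all shifts, inviting every eligible patient until the planned number is reached.
- Re-approach patients missed at one session at a later one. This is feasible because inclusion requires at least 3 months of regular hemodialysis.
- Keep a one-line log per patient (eligible; surveyed; declined or not reached; dialysis age) and report participation by dialysis-age group.

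The cost is one protocol sentence, a roster tick-list and somewhat longer fieldwork for the same researchers, with no increase in the planned number of patients. The documents do not cost this work.

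The plan is unclear on timing: Participants uses the past tense and Data Collection the future. If enrolment is already complete, state that the frequencies and scores describe the surveyed patients, not MHD patients at these centres in general.
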